11.2.3 Listings of Adverse Events

The following listings of AEs will be prepared:

- All serious AEs (from the time the subject signed the study-specific informed consent through the end of the study),
- Treatment-emergent serious AEs,
- Treatment-emergent AEs leading to death,
- Treatment-emergent AEs leading to discontinuation of study drug,
- Treatment-emergent AEs leading to study drug interruption,
- AEs (treatment-emergent or all, as applicable) in each of the AEs of special interest categories,
- Treatment-emergent AIDS-associated OIs.

11.3 Analysis of Laboratory Data

Data collected from the central and local laboratories, including additional laboratory testing due to a serious AE, will be used in all analyses.

11.3.1 Variables and Criteria Defining Abnormality

Hematology variables to be summarized include: hematocrit, hemoglobin, red blood cell (RBC) count, white blood cell (WBC) count, neutrophils, bands, lymphocytes, monocytes, basophils, eosinophils, platelet count, reticulocyte count, prothrombin time (PT), international normalized ratio (INR), and activated partial thromboplastin time (aPTT).

Chemistry variables to be summarized include: blood urea nitrogen (BUN), creatinine, total bilirubin, direct and indirect bilirubin, alanine aminotransferase (ALT), aspartate aminotransferase (AST), alkaline phosphatase, sodium, potassium, calcium, inorganic phosphorus, uric acid, cholesterol, total protein, glucose, triglycerides, albumin, chloride, bicarbonate, magnesium, total insulin, gamma-glutamyl transferase (GGT), creatinine clearance (calculated using Cockcroft-Gault), estimated glomerular filtration rate (eGFR) calculated using the modification of diet in renal disease (MDRD) equation modified for the Chinese population (C-MDRD), and creatinine phosphokinase (CPK).

Urinalysis variables to be summarized include: specific gravity and pH.

The definitions of toxicity grades for laboratory parameters are presented in [Table 15](#).

Table 15. Definitions of Toxicity Grades 1, 2, 3, and 4 for Laboratory Values

Test	Grade 1	Grade 2	Grade 3	Grade 4
ALT	> ULN – 3 × ULN	> 3 – 5 × ULN	> 5 – 20 × ULN	> 20 × ULN
AST	> ULN – 3 × ULN	> 3 – 5 × ULN	> 5 – 20 × ULN	> 20 × ULN
Alkaline Phosphatase	> ULN – 2.5 × ULN	> 2.5 – 5 × ULN	> 5 – 20 × ULN	> 20 × ULN
GGT	> ULN – 2.5 × ULN	> 2.5 – 5 × ULN	> 5 – 20 × ULN	> 20 × ULN
Total Bilirubin	> ULN – 1.5 × ULN	> 1.5 – 3 × ULN	> 3 – 10 × ULN	> 10 × ULN
Hemoglobin	< LLN – 100 g/L	< 100 – 80 g/L	< 80 g/L	--
White blood cells	< LLN – 3.0 × 10 ⁹ /L	< 3.0 – 2.0 × 10 ⁹ /L	< 2.0 – 1.0 × 10 ⁹ /L	< 1.0 × 10 ⁹ /L
Absolute Neutrophil Count	< LLN – 1.5 × 10 ⁹ /L	< 1.5 – 1.0 × 10 ⁹ /L	< 1.0 – 0.5 × 10 ⁹ /L	< 0.5 × 10 ⁹ /L
Platelet count	< LLN – 75.0 × 10 ⁹ /L	< 75.0 – 50.0 × 10 ⁹ /L	< 50.0 – 25.0 × 10 ⁹ /L	< 25.0 × 10 ⁹ /L
INR	> 1 – 1.5 × ULN	> 1.5 – 2.5 × ULN	> 2.5 × ULN	--
Glucose (high)	> ULN – 8.9 mmol/L	> 8.9 – 13.9 mmol/L	> 13.9 – 27.8 mmol/L	> 27.8 mmol/L
Glucose (low)	< LLN – 3.0 mmol/L	< 3.0 – 2.2 mmol/L	< 2.2 – 1.7 mmol/L	< 1.7 mmol/L
Creatinine	> ULN – 1.5 × ULN	> 1.5 – 3 × ULN	> 3 – 6 × ULN	> 6 × ULN
Creatinine clearance	< LLN – 60 mL/min	< 60 – 30 mL/min	< 30 – 15 mL/min	< 15 mL/min
eGFR (C-MDRD)	< LLN – 60 mL/min/1.73 m ²	< 60 – 30 mL/min/1.73 m ²	< 30 – 15 mL/min/1.73 m ²	< 15 mL/min/1.73 m ²
Cholesterol	> ULN – 7.75 mmol/L	> 7.75 – 10.34 mmol/L	> 10.34 – 12.92 mmol/L	> 12.92 mmol/L
Albumin	< LLN – 30 g/L	< 30 – 20 g/L	< 20 g/L	--
Lymphocyte	< LLN – 0.8 × 10 ⁹ /L	< 0.8 – 0.5 × 10 ⁹ /L	< 0.5 – 0.2 × 10 ⁹ /L	< 0.2 × 10 ⁹ /L
aPTT	> ULN – 1.5 × ULN	> 1.5 – 2.5 × ULN	> 2.5 × ULN	--
Sodium (low)	< LLN – 130 mmol/L	--	< 130 – 120 mmol/L	< 120 mmol/L
Sodium (high)	> ULN – 150 mmol/L	> 150 – 155 mmol/L	> 155 – 160 mmol/L	> 160 mmol/L
Potassium (low)	< LLN – 3.0 mmol/L	--	< 3.0 – 2.5 mmol/L	< 2.5 mmol/L
Potassium (high)	> ULN – 5.5 mmol/L	> 5.5 – 6.0 mmol/L	> 6.0 – 7.0 mmol/L	> 7.0 mmol/L

Table 15. Definitions of Toxicity Grades 1, 2, 3, and 4 for Laboratory Values (Continued)

Test	Grade 1	Grade 2	Grade 3	Grade 4
Triglycerides	> 1.71 – 3.42 mmol/L	> 3.42 – 5.7 mmol/L	> 5.7 – 11.4 mmol/L	> 11.4 mmol/L
Magnesium (low)	< LLN – 0.5 mmol/L	< 0.5 – 0.4 mmol/L	< 0.4 – 0.3 mmol/L	< 0.3 mmol/L
Magnesium (high)	> ULN – 1.23 mmol/L	--	> 1.23 – 3.30 mmol/L	> 3.30 mmol/L
CPK	> ULN – 2.5 × ULN	> 2.5 – 5 × ULN	> 5 – 10 × ULN	> 10 × ULN

Assessments of hepatotoxicity will be made based on a single laboratory parameter collected at any post-baseline visit through the Final Treatment visit using the following criteria:

- ALT > 5 × ULN and $\geq 2 \times$ baseline;
- Total bilirubin $\geq 2 \times$ ULN and > baseline;
- Total bilirubin $\geq 2 \times$ ULN and > baseline and direct/total bilirubin ratio > 0.4;
- Increase from nadir by grade in ALT:
 - ALT > 3 – 5 × ULN (Grade 2);
 - > 5 – 20 × ULN (Grade 3);
 - > 20 × ULN (Grade 4).

The direct/total bilirubin ratio will be calculated using the same date/time sample corresponding to the total bilirubin elevation. For the summary of increase from nadir by grade in ALT, the post-baseline value must represent an increase from the first nadir (including baseline) to be counted, where the grade of the post-baseline value must be more extreme than the grade of the nadir value. First nadir is defined as the last value prior to the first increase. The maximum ratio relative to the ULN will be used to determine if subjects meet the criteria listed above.

Assessments of hepatotoxicity will also be made based on multiple laboratory parameters collected at any post-baseline visit through the Final Treatment visit using the following criterion:

- ALT > 3 × ULN (Grade 2 + and increase from nadir grade) and total bilirubin ≥ 2 × ULN.

For the criterion based on multiple laboratory parameters, the analysis will check to see if the subject meets the ALT and total bilirubin portions of the criterion at any time within the Treatment Period (i.e., draw dates do not need to be concurrent). The maximum ratio relative to the ULN for each parameter will be used to determine if the subject meets the criterion listed above. For ALT, the post-baseline value must represent an increase from the first nadir (including baseline) to be counted. First nadir is defined as the last value prior to the first increase. The grade of the post-baseline ALT value must be at least Grade 2 and more extreme than the grade of the nadir value. For total bilirubin, a subject or event will be counted if the post-baseline laboratory values meet the above criteria regardless of the baseline laboratory value (i.e., the post-baseline laboratory value does not need to be worse than the baseline laboratory value).

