#### **6.1.7.1 Management of Increases in ALT**

If a subject experiences a post-baseline increase in ALT to  $> 5 \times \text{ULN}$  which is also  $> 2 \times$  the baseline value, the subject should have a confirmatory ALT measurement performed.

If the ALT increase is confirmed to be  $> 5 \times \text{ULN}$  which is also  $2 \times$  the baseline value, the recommendations below should be followed:

- Complete hepatic questionnaire; evaluate for alternate etiology of ALT elevation; document in the source, update the medical history and concomitant medications eCRF (if applicable), and obtain additional testing as appropriate (e.g., hepatitis B panel, etc.).
- Manage the subject as medically appropriate.
- Repeat ALT, AST, total and fractionated bilirubin, alkaline phosphatase and INR within 1 week. Repeat liver chemistries as indicated until resolution.
- Discontinue study drugs if any of the following is observed at any time:
  - ALT level is  $\geq 20 \times$  ULN in the absence of an alternate etiology.
  - Increasing direct bilirubin or INR or onset of symptoms/signs of hepatitis.
  - At the discretion of the investigator.

Alternate management of ALT increases is permitted with approval of the AbbVie TA MD.

During the DB Treatment Period, if confirmed ALT values meet or exceed predefined toxicity thresholds, refer to Section 5.1.2.

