During the DB Treatment Period, the Final DB Treatment Value is defined separately for placebo and active subjects. Subjects randomized to placebo (Arm B) should take the first dose of OL study drugs the day immediately after the last day of the DB Treatment Period. Therefore, for Arm B subjects, the Final DB Treatment Value is defined as the last non-missing measurement collected after DB Study Day 1 and no more than 2 days after the last dose of placebo and before OL Day 1 (if applicable). For subjects randomized to active study drug (Arm A), the Final DB Treatment Value is defined as the last non-missing measurement collected after DB Study Day 1 and within 2 days of the last dose of active study drug (i.e., on or before Active Study Drug End Day 2).

During the OL Treatment Period, for subjects randomized to placebo who receive OL study drug, the Final OL Treatment Value is defined as the last non-missing measurement collected after OL Day 1 and on or before Active Study Drug End Day 2.

Final Post-Treatment Value

The final PT value for each subject is the last non-missing measurement collected after Active Study Drug End Day 2 and on or before Active Study Drug End Day 999.

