c. The last value within the window will be used to define the Final DB Treatment Visit value. For Arm A subjects, the upper bound of this Final window is DB Study Drug End Day 2. For Arm B subjects, it is the earlier of DB Study Drug End Day 2 and the day of first dose of OL active study drug. DB Study Drug End Day 0 is defined as the day of the last dose of DB study drug.

Note: For all windows, data must be on or before DB Study Drug End Day 2, and for Arm B subjects data must also be on or before the day of first dose of OL active study drug. The result closest to the scheduled time point will be used. PRO instruments are collected at DB Day 1, DB Week 4, DB Week 12 (if 16-week treatment), and DB End of Treatment Visit.

Table 5. Analysis Time Windows for HCV RNA and Resistance Endpoints and Safety Laboratory and Vital Sign Measurements (OL Treatment Period)

Scheduled Visit ^a	Nominal Day (Active Study Day)	Time Window (Active Study Day Range)
OL Day 1 ^b	1	
OL Week 1	7	2 to 10
OL Week 2	14	11 to 21
OL Week 4	28	22 to 42
OL Week 8	56	43 to 70
OL Week 12 ^c	84	71 to 98
OL Week 16 ^c	112	99 to 126
Final OL Treatment Visit ^d	2 to ≤ 2 days after last dose of OL study drug	

- a. OL visits are applicable for subjects randomized to Arm B (placebo) who received at least one dose of OL active study drug.
- b. Day of first dose of OL active study drug. For resistance analyses only, baseline value for Arm B subjects will use the last sample collected before OL Day 1.
- c. For 16-week treatment only.
- d. The last value within the window will be used to define the Final OL Treatment Visit value. The upper bound of this Final window is Active Study Drug End Day 2. Active Study Drug End Day 0 is defined as the day of the last dose of active study drug.

Note: For all windows, data must be on or before Active Study Drug End Day 2. The result closest to the scheduled time point will be used. PRO instruments are not collected for Arm B subjects during the OL Treatment Period.

Analyses of these data will not be included in the primary CSR.

Table 6. Analysis Time Windows for HCV RNA and Resistance Endpoints (Post-Treatment Period)

Scheduled Visit^a	Nominal Day (Active Study Drug End Day)	Time Window (Active Study Drug End Day Range)
Post-Treatment Week 4	28	3 to 56
Post-Treatment Week 12	84	57 to 126
Post-Treatment Week 24 ^b	168	127 to 999
SVR ₄ ^c	28	3 to 56
SVR ₁₂ ^c	84	57 to 126
SVR ₂₄ ^{b,c}	168	127 to 210

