11.0 Safety Analysis

11.1 General Considerations

Safety analyses will be performed on the safety population for data corresponding to DB treatment and on the OL population for data corresponding to OL treatment. Safety data will be summarized for the set of all subjects and for the geographic region of China.

For safety analyses, data from the active (Arm A) and placebo (Arm B) treatment arms during the DB Treatment Period will be summarized, and comparisons between Arms A and B will be performed, as appropriate. Data from the PT Period for Arm A through PT Week 4 will also be summarized for the change from baseline analyses of laboratory parameters, and through PT Week 24 for the change from baseline analyses of vital sign parameters.

Data from the OL Treatment Period and PT Period for Arm B will be not be summarized in the primary CSR, except listings of any serious adverse events and deaths from the OL Treatment Period for Arm B will be included in the primary CSR; these data will be summarized in the interim analysis (following the primary CSR) and in the final CSR.

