Hematology and chemistry data values will be categorized as low, normal, or high based on the normal ranges of the laboratory used for each sample. Shift tables from baseline to minimum value and from baseline to maximum value during the DB and OL Treatment Periods will be created for each treatment arm. The shift tables will cross-tabulate the frequency of subjects with baseline values below/within/above the normal range versus minimum/maximum post-baseline values below/within/above the normal range.

The laboratory parameters listed in [Table 15](#) will be categorized according to the toxicity grades defined in the table. The number and percentage of subjects with a maximum toxicity grade of 1, 2, 3 or 4 during treatment (DB treatment and OL treatment summarized separately) will be calculated for each treatment arm. To be counted, the post-baseline value must have a toxicity grade that is more extreme than the toxicity grade corresponding to the baseline value. For each laboratory parameter in [Table 15](#), the summary will also include the number and percentage of subjects with a maximum of at least Grade 3 for each treatment arm. For summaries of data collected during the DB Treatment Period, the difference in rates between the 2 arms (Arm A minus Arm B), and

the 2-sided 95% CI for the rate difference using the Wilson score method for a difference in proportions will be presented.¹² These summaries will also be presented for the set of HCV/HIV co-infected subjects (determined at Screening) within the populations/groups specified in Section 11.1.

A listing of all relevant laboratory parameters will be provided for each subject who had an increase to Grade 2 or higher for any laboratory variable in Table 15.

For the assessments of hepatotoxicity based on single and multiple laboratory parameters, the number and percentage of subjects meeting the criterion during treatment will be calculated for each criterion. A listing of all ALT, AST, total, indirect and direct bilirubin, ratio of direct to total bilirubin, and alkaline phosphatase values will be provided for each subject who met any of the single or multiple criteria defined above. The listings will be reviewed to assess bilirubin (e.g., mixed or direct predominance) and temporal relationships for subjects with $ALT > 3 \times ULN$ (or ALT Grade 2+) and total bilirubin $\geq 2 \times ULN$.

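### Liver tests drawn more than 2 days after the last dose are left out of every hepatotoxicity count and of the maximum-grade table, and the listings that might show them have no stated time scope

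*SAP*

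**What the plan says.** **Counts and grades**
- SAP 11.3.1, single-parameter criteria: "Assessments of hepatotoxicity will be made based on a single laboratory parameter collected at any post-baseline visit through the Final Treatment visit". These cover ALT > 5 × ULN with at least twice baseline, total bilirubin ≥ 2 × ULN (with and without a direct/total ratio above 0.4), and ALT grade increases from nadir.
- SAP 11.3.1, combined criterion (ALT > 3 × ULN with total bilirubin ≥ 2 × ULN): it also runs through the Final Treatment visit, and its two parts may be met "at any time within the Treatment Period (i.e., draw dates do not need to be concurrent".
- SAP 6.1.2 limits the final double-blind (DB) value in Arm A to one taken "within 2 days of the last dose of active study drug (i.e., on or before Active Study Drug End Day 2". The OL period has the same End Day 2 limit. The note to SAP Table 4 repeats it for DB data: "For all windows, data must be on or before DB Study Drug End Day 2".
- SAP 11.3.2: for hepatotoxicity, "the number and percentage of subjects meeting the criterion during treatment will be calculated for each criterion". Maximum toxicity grades are likewise counted during treatment, DB and OL separately.

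**After treatment**
- SAP 11.1: Arm A post-treatment data "through PT Week 4 will also be summarized for the change from baseline analyses of laboratory parameters". SAP 11.3.2 adds mean-change plots.
- SAP Table 7 assigns one value to PT Week 4, the one nearest Day 28 within Days 3 to 56.
- SAP 11.3.2 plans two by-subject listings. One gives all liver values for anyone meeting a hepatotoxicity criterion. The other gives relevant laboratory values for anyone who rose to Grade 2 or above. Neither states a time limit.
- Protocol 6.1.7.1, after a confirmed ALT rise: "Repeat ALT, AST, total and fractionated bilirubin, alkaline phosphatase and INR within 1 week", with further repeats until resolution. Protocol Appendix C schedules chemistry at PT Week 4.
- SAP 11.2.1 counts adverse events to 30 days after the last dose.

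**The concern.** These criteria are meant to find liver injury from laboratory values alone, without depending on how an investigator words an adverse event. Liver tests can keep rising after the drug is stopped, and the protocol asks for follow-up for that reason. A count that closes 2 days after the last dose can miss the highest ALT and, more importantly, a bilirubin rise that comes after the ALT rise.

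The count most exposed is the combined ALT/bilirubin criterion, because it needs both parts inside the window. SAP 11.3 brings local and SAE-driven laboratory tests into all analyses, but the window still removes those drawn after End Day 2. The SAP does not explain why its laboratory liver counts stop at Day 2 while its hepatic adverse events of special interest run to Day 30.

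**Working it through.** **1. Tracing the limit.** SAP 11.3.1 sends the reader to the Final Treatment visit, and SAP 6.1.2 and Table 4 close that visit at End Day 2. The 2-day limit is confirmed. It is also the more generous reading for the combined criterion, because the protocol's definition of terms ends the Treatment Period at the last dose.

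**2. Comparison with the adverse event window.** 30 − 2 = 28 post-dose days (Days 3 to 30) count for adverse events but not for liver criteria or grades. The scheduled PT Week 4 draw (nominal Day 28) falls here, as can repeat tests after a stop.

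**3. Applying the rules to assumed subjects.** The values are hypothetical. In all three, baseline ALT is 1.5 × ULN (so twice baseline is 3 × ULN), baseline bilirubin is 0.6 × ULN, the ALT nadir is 1.2 × ULN (Grade 1), and the peak is on Day +7 after the last dose. ALT grades follow SAP Table 15: Grade 1 to 3 × ULN, Grade 2 to 5, Grade 3 to 20, Grade 4 above 20. The second cut-off, Day 30, is the adverse event window.

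| Subject | Highest on drug (ALT; bilirubin, × ULN) | Day +7 (ALT; bilirubin) | Through End Day 2 | Through Day 30 |
|---|---|---|---|---|
| A: ALT 6, then 8 on drug | 8; 1.0 | 22; 2.6 | Grade 3; ALT > 5 × ULN met (8 > 5, 8 ≥ 3); combined not met (1.0 < 2) | Grade 4; combined met (22 > 3, 2.6 ≥ 2) |
| B: stopped with ALT 4 | 4; 1.0 | 12; 2.6 | Grade 2; ALT > 5 × ULN not met; combined not met | Grade 3; ALT > 5 × ULN met; combined met |
| C: ALT never above 3 × ULN on drug | 2.5; 1.0 | 12; 2.6 | Grade 1, same as baseline; no criterion met | Grade 3; ALT > 5 × ULN met; combined met |

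**4. Whether PT Week 4 recovers the peak.** It does not. Each subject has a Day 28 value (ALT 2, bilirubin 0.9 × ULN). Its distance from the nominal day is 0, against |7 − 28| = 21 for the peak, so Day 28 is used. Even a high Day 28 value would enter only change-from-baseline summaries and plots; it would not be graded or tested against a criterion.

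**5. Whether the listings recover it.** A and B meet at least one criterion on drug (both through the ALT increase from nadir), so the liver listing, which promises all values, includes them under either cut-off. C meets none on drug and misses the liver listing. Read literally, the Grade 2 listing would include C, because that sentence does not require the increase to occur on treatment. Neither sentence says outright that post-treatment values are shown.

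**6. Subjects stopped under the protocol's ALT rule.** The discontinuation step in Protocol 6.1.7.1 comes after a confirmed ALT above 5 × ULN and twice baseline. One such value on drug already satisfies the first SAP criterion, so these subjects resemble A: counted and listed, but with the later peak missing from the tables.

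**The case against.** Much of the opposing case stands.

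- A reader might infer that a subject withdrawn for liver toxicity vanishes from the laboratory tables and listings. The documents do not support this. Such a subject is in the ALT > 5 × ULN row and in the liver listing, and SAP 11.3.2 says the listings will be reviewed for bilirubin pattern and timing where ALT and bilirubin are both raised.
- A reader might also infer that repeat tests in these subjects always fall after End Day 2. Protocol 6.1.7.1 times the repeat from the confirmed rise, not from the last dose. The discontinuation visit includes chemistry and should take place within 2 days of the last dose (Protocol 5.4.1). A value of 20 × ULN that triggers stopping on drug is itself counted. Late values are possible, not certain.
- Adverse event reporting covers part of the gap. A laboratory value that requires discontinuation is recorded as an adverse event (Protocol 5.3.1.1), and events are collected and summarized to Day 30. Cover is incomplete, because Protocol 6.1.1.1 makes a laboratory abnormality an adverse event only under listed conditions or on the investigator's judgement.
- Protocol 8.1.5.2 itself confines graded values to the treatment periods, and Arm B starts active drug the day after the DB period, so there is no placebo interval to match. This justifies End Day 2 for the Arm A versus Arm B comparison. It does not justify it as the only count. The OL population has no comparator, and the hepatotoxicity criteria were added by the SAP (section 12.1), so the protocol sets no window for them.

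**Conclusion.** The point holds for the tables, not for the listings. ALT and bilirubin values after End Day 2 enter no hepatotoxicity count and no toxicity-grade count. They appear at most in two listings whose time scope is unstated. The tables lose three things: a later higher grade, a later bilirubin rise and with it the combined criterion, and any subject who first qualifies after End Day 2.

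In the assumed cases the combined count goes from 0 of 3 to 3 of 3, and the maximum ALT grade rises by one step in A and B and by two in C. These cases show how the rule works; they do not estimate frequency, and the documents give no rate for such events. One subject among the planned 336 in Arm A is 1/336 = 0.3%. If events are that rare, a single late case could move the combined count from zero to one. A reader might extend that to the ALT > 5 × ULN row, but for subjects stopped under the ALT rule that row already counts them.

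This is a cheap improvement to the safety tables and does not undermine the planned comparison of the arms.

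**What to change.** In SAP 11.3.1 and 11.3.2:

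1. Keep the End Day 2 analysis as it is for comparing Arm A with Arm B, so that observation periods stay equal.
2. Add a descriptive count of every hepatotoxicity criterion, and of Grade 3 or higher ALT, AST and total bilirubin, using all values through 30 days after the last dose of active drug, for Arm A and for the OL population.
3. State that both by-subject listings include post-treatment values, and subjects who first qualify within those 30 days.

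The cost is a few sentences and one more run of existing tables, with no new data collection. The extended count has no matching placebo interval, so it should be labelled descriptive and shown beside the on-treatment comparison. Because the PT Week 4 window runs to Day 56, a draw taken after Day 30 would still fall outside this count; Day 30 is used here because it is the plan's own adverse event limit.

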11.3.2 Statistical Methods

Clinical laboratory tests will be summarized by treatment arm (A and B) at each visit during the DB Treatment Period and separately for Arm B subjects during the OL Treatment Period. Also, summaries of clinical laboratory data collected during the Post-Treatment Period will be presented for Arm A of the safety population and separately for the OL population.

The baseline value for clinical laboratory tests will be the last non-missing measurement on or before the day of the first dose of DB study drug. Values on Day 1 must also be before the time of first dose if time is available. The same baseline value will be used for all summaries of the data from the DB, OL, and Post-Treatment Period visits.

Changes from baseline to each post-baseline visit, including applicable post-treatment visits, will be summarized. For DB Treatment Period visits and for Post-Treatment visits for Arm A, each protocol-specified laboratory parameter will be summarized with the sample size; baseline mean; visit mean; and change from baseline mean, standard

deviation, and median. The differences between the active and placebo arms in the DB Treatment Period will be analyzed using an ANOVA model with treatment arm as the factor. The difference between the treatment arms (Arm A minus Arm B) in mean change from baseline along with the corresponding 95% CI, standard error, and *P* value will be presented. For OL Treatment Period visits and Post-Treatment visits for Arm B, each protocol-specified laboratory parameter will be summarized with the sample size; baseline mean; visit mean; and change from baseline mean, standard deviation, minimum, median, and maximum.

Plots of mean change (\pm standard error) from baseline to each visit will be presented by treatment arm for ALT and bilirubin (total, direct, and indirect). For each parameter, mean changes at visits during the DB Treatment Period for Arms A and B along with mean changes at post-treatment visits for Arm A will be presented on the same plot, and mean changes at visits during the OL Treatment Period will be provided for Arm B on a separate plot.

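### The ALT first-nadir reference is never lowered after the first uptick, so a flare that follows later normalisation can drop out of the hepatotoxicity counts

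*SAP*

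**What the plan says.** SAP 11.3.1 defines the hepatotoxicity criteria. For the ALT grade-increase criterion, "the post-baseline value must represent an increase from the first nadir (including baseline) to be counted". A rise within one grade band is not enough: the later result has to fall in a higher band than the reference. How that reference is chosen is stated next: "First nadir is defined as the last value prior to the first increase".

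The criterion that combines ALT above 3 × ULN with total bilirubin of at least 2 × ULN uses the same reference: "For ALT, the post-baseline value must represent an increase from the first nadir (including baseline) to be counted".

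Two other ALT counts exist. Both refer to baseline:
- SAP 11.3.1 counts ALT above 5 × ULN that is also at least twice baseline.
- The toxicity-grade summary in SAP 11.3.2 applies the condition that "the post-baseline value must have a toxicity grade that is more extreme than the toxicity grade corresponding to the baseline value".

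On periods, SAP 11.3.2 summarises double-blind and open-label laboratory data separately but keeps one baseline: "The same baseline value will be used for all summaries of the data from the DB, OL, and Post-Treatment Period visits". It does not say whether the nadir search for Arm B restarts at OL Day 1.

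**The concern.** A nadir-based ALT criterion is useful because many subjects enter with raised ALT. Protocol 5.2.2 excludes only ALT above 10 × ULN, so Grade 2 and Grade 3 baselines are possible. Protocol 3.0 reports that raised ALT moved toward normal on treatment. In such a subject a count against baseline cannot show a rise from normal back to, say, 8 × ULN. A count against the nadir should.

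The SAP's definition can defeat that purpose. Any uptick, however small, ends the search. If it comes before ALT normalises, the reference stays high and the later flare is measured against it. The counts affected are the trial's pre-specified liver-safety summaries, including the combined ALT and bilirubin criterion.

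**Working it through.** The documents give no figure for this rule, so there is nothing to reproduce. The check applies the rule to worked profiles, then sizes it by simulation.

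**Inputs from the documents.** ALT grades (SAP 11.3.1 and Table 15): Grade 2 is > 3–5, Grade 3 > 5–20 and Grade 4 > 20 × ULN. Visits in an 8-week double-blind period: Day 1 and Weeks 1, 2, 4 and 8 (protocol synopsis). Planned Arm B size: 168 (SAP Table 1).

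**Step 1: worked profiles (× ULN).**

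| Profile | First nadir | First-nadir rule | > 5 × ULN and ≥ 2 × baseline | Grade above baseline | Running minimum |
|---|---|---|---|---|---|
| 6, 2, 0.8, 0.7, 8 | 0.7 | counted | missed | missed | counted |
| 6, 6.5, 2, 0.8, 8 | 6 (Grade 3) | missed | missed | missed | counted |
| 3.3, 3.4, 0.8, 0.8, 4.8 | 3.3 (Grade 2) | missed | missed | missed | counted |
| 6, 3.5, 3.6, 0.8, 4 | 3.5 (Grade 2) | missed | missed | missed | counted |

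The first two rows end in the same flare. They differ in an early uptick from 6 to 6.5.

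**Step 2: which flares are lost.** A flare is lost only if its grade is no higher than that of the first nadir, so the first nadir must be Grade 2 or above. From a reference of 4, a flare to 9 × ULN is counted. From 6, a flare to 21 × ULN is counted.

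**Step 3: do the other ALT counts recover them?** Values do not rise before the first nadir, so the first nadir is never above baseline. A flare lost under the nadir rule therefore has a grade no higher than baseline's, and the baseline-referenced grade table cannot count it. The doubling criterion recovers a lost Grade 3 flare only if it is at least twice a baseline that is itself above 5, hence above 10 × ULN. In 6, 6.5, 2, 0.8, 13, for example, 13 ≥ 2 × 6 = 12.

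**Step 4: where it could concentrate.** Arm A starts active drug on Day 1, so the search usually follows ALT down. An Arm B subject has five values before active drug. If these are exchangeable, the chance of no uptick is 1/5! = 1/120 = 0.8%. If one search runs on from the double-blind baseline, about 99% of Arm B references are fixed before open-label drug. If it uses baseline plus open-label visits, Arm B behaves like Arm A.

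**Step 5: size, under assumed values.** The documents give no ALT distribution. Assumptions: baseline median 1.6 × ULN, log SD 0.7, within-subject log SD 10–30%, ALT falling to about 40% on drug, and one late flare. Results are the percentage of flares missed.

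| Setting | Overall | Baseline > 3 × ULN |
|---|---|---|
| Arm A | 0–2% | up to 4% |
| Arm B open-label, search continues through placebo, flare uniform on 3.2–12 × ULN | about 5–6% | about 25–35% |
| Same, across a second simulation on the same baseline, variability and decline assumptions | 3–12% | 16–65% |
| Arm B open-label, baseline plus open-label visits only | 0–3% | not tabulated |

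A further simulation fixed pre-treatment ALT at 4 or 7 × ULN, with visit-to-visit CV 10–30% and a flare to 4.5 or 8 × ULN. With a continuing search, Arm B missed 62–99% of flares in the same or a lower grade band than pre-treatment ALT. It missed 0–3% when the flare was in a higher band (4 to 8 × ULN). Arm A, and Arm B with a restarted search, missed 0–3%. A running minimum missed none.

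**The case against.** The strongest reply is that the Arm B problem rests on a reading the SAP does not state. Much of the surrounding text is period-specific. SAP 6.1.2 and Tables 4 and 5 define separate final double-blind and final open-label values. SAP 11.1 analyses double-blind data on the safety population and open-label data on the OL population. The single-baseline sentence in 11.3.2 does not bring placebo visits into an open-label nadir.

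This stands, but it does not settle the matter. No restart is written. The combined criterion looks anywhere within the Treatment Period, which protocol 1.2 defines as Day 1 through the last dose of study drug. A programmer could do either.

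Other limits also stand:
- The percentages are conditional on a late flare occurring. Protocol 3.0 reports no on-treatment ALT elevation above baseline in the two Phase 2 studies, and no expected number of missed subjects can be derived.
- Open-label laboratory summaries are not in the primary CSR (SAP 11.1).
- A subject whose bilirubin is at least 2 × ULN and above baseline meets a criterion without any ALT nadir. That subject's liver values are listed, and the listings are reviewed for the combined pattern (SAP 11.3.2). Isolated ALT flares have less cover, and a listing is not a count.
- The definition came from the wider program (SAP 12.1, item 18), and a running minimum counts more placebo fluctuation.

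A reader might infer that the rule biases the randomised safety comparison in the drug's favour, or that open-label flares in Arm B are shown to be lost. The documents support neither. Loss in Arm A is small, and the Arm B loss depends on an unstated choice.

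**Conclusion.** The defect in the definition holds on the SAP's wording alone: the reference is not updated, and a flare after normalisation is uncounted when its grade is no higher than that of a Grade 2 or higher first nadir. The worked profiles need no outside assumption.

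The size does. Under the assumed distributions it is about 0–4% of flares in Arm A. In the Arm B open-label period it is about 5–6% overall and 25–35% with baseline above 3 × ULN, but only if the search continues through placebo; otherwise it is rare. This is a cheap improvement to a liver-safety count and an ambiguity to close. It is not a demonstrated bias of the double-blind comparison. Any open-label effect falls on the interim and final analyses.

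**What to change.** In SAP 11.3.1, define the ALT nadir as the lowest value from baseline up to the visit before the one assessed. Apply it to both the single-parameter grade-increase criterion and the combined ALT and bilirubin criterion. State that for the open-label period the search starts at the last value before OL Day 1. The single baseline in 11.3.2 can remain for change-from-baseline and toxicity-grade summaries. If alignment with the program is needed, show the first-nadir count alongside.

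The cost is one definition, minor programming and a second reference value for Arm B. More fluctuation will be counted, mostly on placebo. In a simulation of the double-blind period without flares, on the same kind of assumptions with baseline capped at 10 × ULN, the placebo count rose from 9.3% to 10.5% (within-subject SD 10%) and from 26.1% to 27.8% (SD 30%), that is by 1.2 and 1.7 percentage points. The active arm stayed at 0.4% and rose from 4.0% to 4.3%. This slightly widens the double-blind contrast in the drug's favour, which is another reason to show both counts. Data collection, the primary endpoint and subject management are unaffected.
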